7.2 Screening and Randomization

At the baseline visit, informed consent will be obtained and eligibility confirmed by the research coordinator and study physician. A subsequent randomization/treatment visit will then be scheduled within a 2 week time period. Several factors may be associated with naltrexone treatment success/failure. We will stratify urn randomization by gender and recruitment status (in-clinic vs. community referrals). Stratifying further, however, yields increasingly smaller cells, given 117 per arm; AA ethnicity, medication preference (monthly injectable vs. daily oral), and lead-in (3-day) abstinence will be analyzed as a priori predictors of effectiveness. Randomization is the starting point of the study (day 1, week 1).

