7.3 Study Interventions: Medical Management plus XR-NTX vs. O-NTX

Existing primary care physicians, all board-certified in internal medicine, physician assistants, and registered nurses at an adult primary care clinic, Bellevue Hospital, will be recruited to participate in this trial as MM clinicians. As in our previous studies with XR-NTX and buprenorphine in these sites, study participants may see different individual providers over the course of 24 weeks, thus optimizing visit flexibility as well as enhancing generalizability to multi-provider practice settings. The same study clinicians will provide both XR- and O-NTX treatment. The study site relies primarily on physician visits as the core modality for primary care encounters, and it is expected study visits will be primarily with physicians. Study clinicians will provide all XR-NTX injections in clinic (Ambulatory Care, 2nd floor, Rm. #2111) each month for each participant randomized to the XR-NTX arm. O-NTX, which is a daily oral pill formulation of naltrexone, will be self-administered on a daily basis by O-NTX participants.

The content of the Medical Management component will be the same in both arms, and will be based on the initial and follow-up MM visits outlined in the COMBINE MM manual and adapted by the NIAAA Clinician's Guide.²⁰ MM emphasizes: a) education surrounding the alcohol dependence diagnosis, b) a recommendation and emphasis on drinking abstinence, c) support for 12-step involvement (referrals to specialty outpatient treatment will not be part of the MM strategy – patients interested in such will not be prohibited from self-referral, and specialty referrals will be made in cases of relapse/treatment failure), d) self-efficacy counseling surrounding medication adherence, e) education and trouble-shooting of medication side effects, f) feedback on the success of drinking reductions, g) and non-specific support and motivational enhancement to make further changes toward abstinence.

MM clinician's will be trained at start-up and through quarterly calls and booster session in an adaptive approach consistent with the NIAAA COMBINE trial (see NIAAA COMBINE manual) and in consultation with [name]. Strict standardization and certification of MM clinicians, as was done in COMBINE, will not be pursued, as this would diverge from a pragmatic clinical trial attempting to reflect the adoption of, but not absolute fidelity to COMBINE MM.

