7.8 Rescue Strategies among Treatment Non-Responders

Clearly many outcomes will occur among the 234 planned participants, beyond drinking reductions, and include: remaining in treatment and tolerating either medication but without beneficial changes to baseline alcohol intake levels; dropping out of all treatment but reporting diminished drinking; or wishing to remain in primary care treatment but unable to tolerate either form of naltrexone. Regarding continued heavy alcohol use, MM already informs and encourages interested patients to access AA, and this recommendation would be particularly relevant to those not responding to pharmacotherapy and amenable to an external referral to more intensive treatment. At any point in the trial, patients who appear to be unable to stop drinking due to severe withdrawal symptoms or who are experiencing severely detrimental consequences of heavy drinking (i.e., job loss, homelessness) will be encouraged to seek admission to inpatient detox and specialty treatment through Bellevue Hospital. Detox and intensive outpatient alcohol specialty services are immediately available to all participants through the Bellevue Hospital Chemical Dependency programs, including same-day admissions to our detox unit, regardless of insurance status or ability to pay. All enrolled participants, however, will be encouraged to remain in their assigned treatment protocols and continue follow-up in primary care for the entire 24 week treatment period, independent of medication side effects, on-going drinking, or intermittent detox or other alcohol-related inpatient treatment episodes. There is little risk, in other words, at keeping participants engaged in primary care MM regardless of on-going, frequent heavy drinking, in which case they would qualify as a primary good clinical outcome failure, or the need for further, more intensive specialty treatment, access to which the MM clinician and study staff may be crucial in facilitating. At the conclusion of the 24 week treatment trial, all patients will be offered further primary care follow-up within the same clinics and referrals to specialty alcohol treatment, if indicated, through these universally accessible addiction specialty services at Bellevue Hospital.

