The primary outcome measure of this study is a binary measure of success defined by abstinence or moderate drinking only, as measured by the TLFb, with drop-outs from MM and research-only assessments assumed to have resumed baseline rates of heavy drinking, and therefore defined as good clinical outcome failures. Our analytic approach will be an intention-to-treat comparison of all randomized participants (N=234). The analysis will utilize a logistic regression with an indicator variable for treatment and covariate terms for baseline potential prognostic indicators that are not stratified for at randomization, including AA ethnicity, lead-in abstinence, medication preferences, baseline drinking severity, in-trial specialty treatment involvement, clinical site, and OPRM1 genotype. If the coefficient of treatment is significant the null hypothesis of equal treatment effect is rejected. Odds ratios will be calculated to quantify the risk to treatment failure of significant predictors (Secondary Aim 2: Patient-Level Predictors of Effectiveness: To identify patient-level characteristics associated with effectiveness in both arms). To differentiate time to a good clinical outcome failure, we will use a "cure model." The form of a cure model is $H(t) = 1 - p + pS(t)$; where $H(t)$ is the probability of failure at a time greater than t , p represents the probability of failure, and $S(t)$ the distribution of time to failure, conditional on failure occurring. The parameters will be estimated based both on Kaplan Meier methods and parametrically. The equality of the values of p for the two treatment arms will be tested using a nonparametric likelihood ratio test. For the parametric test, a logistic will be used to model p and a Weibull survival distribution will be used to model time to failure, $S(t)$. Both allow the use of covariates, which will complement the above logistic regression approach.

As originally proposed, naltrexone appears most effective at reducing heavy drinking, as opposed to producing complete abstinence, and all traditional alcohol treatment trial clinical endpoints, including continuous drinking and heavy drinking variables, as well as the CDT biomarker, which is specific for heavy drinking, are of great interest, and will be reported in the primary publication from this trial. In addition, rates

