If the trial is negative, what’s the purpose of Aim 2? It might be observed that, if an intervention is not effective, it is meaningless to estimate its cost-effectiveness. Therefore, it might appear that the scientific validity of Aims 1 and 2 are inter-dependent. However, in the event that Aim 1 produces negative results, we will employ the computer simulation developed for Aim 2 for a slightly different purpose. Rather than using the simulation to estimate the cost-effectiveness of XR-NTX versus O-NTX, we will instead use the simulation to ask “what is the minimum level of incremental effectiveness required for an intervention to deliver sufficient value?” so that Aim 2 remains scientifically relevant and useful for decision makers. For example, even if XR-NTX does not deliver significant improvements in effectiveness compared to O-NTX, we would use the simulation to infer what levels of incremental effectiveness would be necessary to deliver sufficient value, given particular assumptions about incremental costs. For example, if a new intervention cost \$100/month more than O-NTX, how many fewer heavy-drinking days would it need to reduce compared to O-NTX in order to deliver sufficient value (incremental cost-effectiveness ratio < \$100,000/QALY)? That way, simulation results can inform future trial design. This approach is detailed in our recent publication,⁹⁸ and is concordant with principles of value-of-information analysis.⁹⁹

10.3 Secondary Aim 2: Patient-Level Predictors of Effectiveness. The multivariate models described for Aim 1, while testing the main and subsidiary hypotheses, will also be used to identify patient characteristics associated with treatment success. We hypothesize a priori that there will be less robust effectiveness in both arms among women and African Americans, while pre-treatment abstinence, voluntary specialty alcohol treatment and Alcoholics Anonymous involvement (patients are not directly referred to ancillary treatment), and presence of the Asp40 OPRM1 SNP will be associated with treatment effectiveness. We also hypothesize that these positive associations will be more pronounced within the XR-NTX arm due to the sustained medication adherence following each injection. We note, however, that these analyses will be exploratory, as the study is not powered to carefully test these secondary hypotheses.

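### The primary logistic model adjusts for in-trial specialty treatment, a post-randomisation variable that relapse can trigger, so its treatment coefficient is not a valid intention-to-treat effect.

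*Combined protocol and SAP*

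**What the plan says.** Section 10.1 specifies an intention-to-treat comparison of all 234 randomised participants by logistic regression. The model has a treatment indicator and "covariate terms for baseline potential prognostic indicators that are not stratified for at randomization". The list that follows includes "baseline drinking severity, in-trial specialty treatment involvement, clinical site, and OPRM1 genotype". The decision rule is: "If the coefficient of treatment is significant the null hypothesis of equal treatment effect is rejected".

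Section 7.2 sets randomisation as day 1 of the study, so anything recorded in-trial comes after it.

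Two sections describe how participants reach specialty care because of drinking. Section 7.3 (Medical Management content) states that "specialty referrals will be made in cases of relapse/treatment failure". Section 7.8 says that participants with severe withdrawal or severely harmful consequences of drinking "will be encouraged to seek admission to inpatient detox and specialty treatment through Bellevue Hospital".

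Section 10.3 describes the same behaviour differently, as "voluntary specialty alcohol treatment and Alcoholics Anonymous involvement", and adds that participants are not directly referred to it.

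**The concern.** The covariate list contradicts its own label, because an in-trial variable is not a baseline indicator. The secondary mixed-model analyses in the same section adjust for baseline variables only, so the confirmatory test is held to a looser standard than the supporting ones.

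The variable is also tied to the outcome. If relapse leads to referral, failure on the primary endpoint is one cause of the covariate. Assignment may affect it as well: Medical Management clinicians see participants while they are retained, and section 9.0 expects 40-50% of XR-NTX participants to complete 24 weeks against under 20% on O-NTX.

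Adjusting for a variable that depends on both arm and outcome can move the odds ratio away from its true value in either direction, and the p-value with it. Including all 234 participants does not repair this, because the comparison is made within levels of something that happened after assignment.

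**Working it through.** **Inputs from the documents.** 117 per arm; success 20% on O-NTX and 40% on XR-NTX (section 9.0). The planned odds ratio is (0.40/0.60)/(0.20/0.80) = 2.667.

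**Assumptions.** Two-sided alpha of 0.05, which the plan does not state. Write M for in-trial specialty involvement, *f* for its probability among failures in an arm and *s* for its probability among successes. The documents give neither *f* nor *s*, so they are varied.

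**The plan's own figure.** Exact two-sided Fisher power for 20% against 40% is 0.844 at 100 per arm (stated 0.84) and 0.901 at 117 per arm (stated 0.90). Both reproduce, but they describe an unadjusted test, not the adjusted model in section 10.1.

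**Why the adjusted odds ratio can move.** By Bayes' rule, within an arm:

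- odds(success | M=1) = odds(success) × *s*/*f*
- odds(success | M=0) = odds(success) × (1−*s*)/(1−*f*)

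If *s* and *f* are the same in both arms, the multipliers cancel and the treatment odds ratio is unchanged. If they differ by arm, they do not cancel.

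Example with no true effect: *s* = 0.10 in both arms, *f* = 0.50 (XR-NTX) and 0.25 (O-NTX).

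- M=1: (0.10/0.50)/(0.10/0.25) = 0.20/0.40 = 0.50
- M=0: (0.90/0.50)/(0.90/0.75) = 1.80/1.20 = 1.50

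The true odds ratio is 1.00. The model fits one coefficient across both strata. Since 90% of successes have M=0, it settles at about 1.30.

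**Size over a range.** The table gives the large-sample limit of the logistic model with treatment and M, scaled to 234 participants. Rejection is type I error in the rows with 30% success in both arms, and power in the rows with 20% against 40%.

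| Success O / XR | *s* | *f* O / XR | Adjusted OR | Rejection |
|---|---|---|---|---|
| 30 / 30% | 10% | 30 / 35% | 1.04 | 5.3% |
| 30 / 30% | 10% | 30 / 40% | 1.10 | 6.2% |
| 30 / 30% | 10% | 25 / 50% | 1.30 | 13.8% |
| 30 / 30% | 10% | 20 / 60% | 1.59 | 31.8% |
| 30 / 30% | 10% | 50 / 25% | 0.77 | 13.8% |
| 30 / 30% | 40% | 25 / 50% | 0.98 | 5.0% |
| 20 / 40% | 10% | 40 / 40% | 2.667 | 0.88 |
| 20 / 40% | 10% | 60 / 60% | 2.667 | 0.835 |
| 20 / 40% | 5% | 30 / 50% | 3.53 | 0.974 |
| 20 / 40% | 5% | 50 / 30% | 2.04 | 0.611 |

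Without M, the same method gives 5% under no effect and power 0.908 with an odds ratio of 2.667. Simulation of thousands of trials at 117 per arm agrees: for the 25/50% and 20/60% rows, type I error is about 13-14% and 32-33% with M, and 4-5% without it.

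**The case against.** The strongest reply is that bias is not inevitable. With equal involvement by arm given outcome, the odds ratio stays at 2.667 and only power is lost. Small gaps do little. If involvement were common among successes too, as in the 40% row, the distortion nearly vanishes. All of this stands.

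The retention figures do not by themselves produce the large gaps. Section 9.0 reports that 36 of 40 pilot completers (90%) succeeded. Apply 90% to completers in both arms and assume no success among drop-outs. Completers who fail are then 0.04/0.64 = 6% to 0.05/0.55 = 9% of XR-NTX failures, against 0.02/0.82 = 2% of O-NTX failures. Most failures in both arms are drop-outs, and the documents give no rate of referral before they leave. Section 12.1 also reports that none of the 72 pilot patients was referred to detox, although that covers detox only and a shorter treatment. So 50% or 60% among failures is illustrative.

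Relapse referral is also only one route. The same sentence in section 7.3 says specialty referral is otherwise not part of Medical Management and allows self-referral, and section 10.3 calls involvement voluntary. Voluntary involvement is still post-randomisation.

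Equal involvement by arm is, however, not what the plan expects. Section 10.3 hypothesises that the association between specialty involvement and success will be stronger in the XR-NTX arm. If that association differs by arm, involvement given outcome must differ by arm too.

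Two features are offered as mitigation. The covariate screening in section 10.0 might drop the variable, but it favours strong predictors, and section 3.6 reports a strong pilot association for specialty and AA involvement. The cure-model test of equal failure probability could expose a discrepancy, but it does not carry the stated rejection rule.

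**Conclusion.** The concern holds. As written, the confirmatory test conditions on a variable that arises after randomisation and is partly a consequence of the outcome. Its coefficient is not the effect of assignment that the plan claims to estimate, and no logistic analysis limited to baseline covariates is specified beside it.

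The error in the model is certain; its numerical effect is not. Over the assumed involvement rates it runs from negligible to a type I error of about 32%, in either direction. Under the planned effect, power ranges from about 0.61 to 0.97, with the odds ratio displaced to between 2.04 and 3.53. With equal involvement the cost is power alone. Because neither sign nor size can be known in advance, a significant or a null result could not be attributed to assignment. This should be corrected before the analysis.

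**What to change.** Delete in-trial specialty treatment involvement from the primary model in section 10.1, and state that its covariates are limited to values fixed before randomisation. Apply the same limit to any covariates in the parametric cure model. If adjustment for help-seeking is wanted, use specialty or AA involvement recorded at or before baseline.

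Report in-trial specialty care by arm as a descriptive outcome. Keep its association with success in exploratory Secondary Aim 2, labelled as post-randomisation and non-causal. Reconcile the account of referral in sections 7.3 and 7.8 with that in section 10.3, so that the variable has one definition.

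The cost is one line of analysis wording for the primary model and short edits elsewhere. No new data are needed.

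### The primary logistic model in section 10.1 adjusts for in-trial specialty treatment, which arises after randomisation and is partly triggered by treatment failure

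*Combined protocol and SAP*

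**What the plan says.** Section 10.1 plans an intention-to-treat comparison of all 234 randomised participants by logistic regression, with a treatment indicator and "covariate terms for baseline potential prognostic indicators" that were not stratification factors. The list ends with "baseline drinking severity, in-trial specialty treatment involvement, clinical site, and OPRM1 genotype". The decision rule follows: "If the coefficient of treatment is significant the null hypothesis of equal treatment effect is rejected".

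Section 7.2 defines randomisation as day 1 of week 1, so anything recorded in-trial comes after it.

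Two parts of the care plan link specialty treatment to poor outcome. Section 7.3 keeps specialty referral out of routine Medical Management (MM) but adds that "specialty referrals will be made in cases of relapse/treatment failure". Section 7.8 has staff encourage detox and specialty treatment for patients who appear unable to stop drinking because of severe withdrawal, or who suffer severe consequences of heavy drinking.

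Section 10.3 states that the same models "will also be used to identify patient characteristics associated with treatment success". It describes specialty involvement there as voluntary, adding in parentheses that "patients are not directly referred to ancillary treatment".

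**The concern.** A covariate in a randomised comparison is safe when neither treatment nor outcome can affect it. This one can be affected by both. A patient who relapses and is then referred counts as involved because of the failure that the model is trying to explain. Adjusting for it compares arms within groups that are partly defined by outcome.

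This matters because the affected coefficient decides the trial. Unequal referral is possible: the trial is open-label, MM clinicians make the referrals, and section 9.0 predicts 24-week completion of 40-50% on XR-NTX against under 20% on oral naltrexone, so contact with referring clinicians may differ by arm. That is inference, and it does not say which arm would be referred more.

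**Working it through.** **Inputs from section 9.0.** Success is 20% (oral) and 40% (XR-NTX), with 117 per arm. Alpha is not stated; 0.05 two-sided is assumed.

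**The plan's own figure.** Exact enumeration of Fisher's test gives power 0.844 at 100 per arm (stated 0.84) and 0.901 at 117 per arm (stated 0.90). The stated power is reproduced. It belongs to an unadjusted test.

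**Unadjusted odds ratio.** (0.4/0.6)/(0.2/0.8) = 2.67.

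**Case 1: involvement S depends only on final outcome Y, equally in both arms.** By Bayes' rule, logit P(Y=1 | T,S) = logit P(Y=1 | T) + log[P(S | Y=1)/P(S | Y=0)]. The last term does not contain treatment T, so the odds ratio stays 2.67. Only power can fall: in simulation it is 0.92 with 10% or 20% of failures referred, and 0.87-0.89 with 50%.

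**Case 2: referral of failures differs by arm.** Let s be the share involved on their own initiative and r the share of the other failures who are referred. Then:
- among the uninvolved, OR = 2.67 × (1 − r_oral)/(1 − r_XR)
- among the involved, OR = 2.67 × [s + (1 − s)r_oral]/[s + (1 − s)r_XR]

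With s = 0.10, r_oral = 0.40 and r_XR = 0.20, these are 2.67 × 0.60/0.80 = 2.0 and 2.67 × 0.46/0.28 = 4.4. Most patients are uninvolved, so the single adjusted estimate lies nearer the lower value: 2.25 in simulation.

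Simulated trials (10,000 to 20,000 per setting, 117 per arm) used a likelihood-ratio test of treatment. Each cell gives results for self-initiated involvement of 10% / 25% (among failures, in the last column). All referral rates are assumptions.

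| Failures referred, oral/XR-NTX | True success, oral/XR-NTX | Self-initiated involvement unrelated to success | Odds ratio 2 with success |
|---|---|---|---|
| 40%/20% | 20%/40% | power 0.75 / 0.84, OR 2.25 / 2.44 | power 0.83 / 0.90, OR 2.4 / 2.6 |
| 20%/40% | 30%/30% | error 9.8% / 6.6% | error 7.3-7.7% / 5.2-5.5% |
| 10%/20% | 30%/30% | error 5.4% / 5.1% | error 5.0% / 5.4% |

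Without the covariate, power is 0.92-0.93 and error 4.8-5.4%. The bias can also go upward: under the planned effect, 20%/40% referral with unrelated involvement gives odds ratios of 3.28 / 3.02.

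**Case 3: referral follows early relapse, which treatment reduces, at the same rate in both arms.** Assume success of 5% after early relapse and 60% otherwise. Early relapse must then be 0.40/0.55 = 73% (oral) and 0.20/0.55 = 36% (XR-NTX) to give 20% and 40% success. Assume also 5% specialty use without relapse and no effect of S on drinking. Referral of 20%, 40% and 60% after relapse gives large-sample odds ratios of 2.59, 2.40 and 2.13, with Wald power 0.89, 0.81 and 0.67, against 2.67 and 0.91 unadjusted. Equal referral alone therefore does not guarantee an unbiased odds ratio.

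**The case against.** The best case against giving this weight is about size, and much of it stands.

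- **The larger distortions need high, unequal referral.** Nothing documents a two-fold difference between arms. Section 7.3 gives both arms the same clinicians and MM content. Section 10.1 counts drop-outs as failures, and section 9.0 sets success close to adherence, so many failures will have left MM and could be referred only before leaving.
- **The nearest evidence is low.** Section 12.1 reports 0 of 72 pilot patients referred to detox, a one-sided 95% upper limit of 1 − 0.05^(1/72) = 4.1% per patient. Section 9.0 reports 36 pilot successes; counting the other 36 patients as failures, the limit per failure is 1 − 0.05^(1/36) = 8.0%. This covers detox only, on XR-NTX only, over three months.
- **The protocol expects involvement to go with success** (sections 3.6 and 10.3). That offsets failure-triggered referral, as the last column of the table shows.

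Other replies do not remove the problem. The voluntary wording in section 10.3 describes an exploratory hypothesis; it neither limits the section 10.1 covariate nor withdraws the section 7.3 rule. Section 10.0 screens covariates on predictive importance, which makes entry conditional but would tend to favour a variable triggered by failure. Section 10.1 also has a nonparametric cure-model test, apparently without covariates, but the decision rule is attached to the logistic coefficient.

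A reader might also infer that section 7.8 directs all non-responders to specialty care. It does not: the sentence containing "particularly relevant to those not responding to pharmacotherapy and amenable to an external referral to more intensive treatment" is about the recommendation to attend Alcoholics Anonymous (AA). The relevant text is the narrower encouragement towards detox and specialty treatment.

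**Conclusion.** The point holds. A post-randomisation variable, partly produced by failure, is in the model that decides the primary hypothesis, so the adjusted coefficient is not the stated intention-to-treat effect. That much rests on the text alone. The size rests on assumed referral rates and ranges from negligible to material, as the table shows; low rates look more likely.

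Three stronger conclusions are tempting and unsupported:
- **That the primary result will be biased in a known direction, or its error rate materially inflated.** The documents give no referral rates by arm.
- **That the stated power is wrong.** It is reproduced for the test named in section 9.0.
- **That section 10.3 needs redesign.** The protocol says of it that "these analyses will be exploratory, as the study is not powered to carefully test these secondary hypotheses", and a caution is enough.

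**What to change.** In section 10.1, delete in-trial specialty treatment involvement from the primary logistic model and from any covariate-adjusted cure model used to compare arms. Keep only pre-randomisation covariates. Specialty or AA involvement at randomisation may take its place if it is available.

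In-trial involvement can stay in the exploratory Secondary Aim 2 analysis, with a note that clinician referral after failure (section 7.3) can itself produce an association with failure.

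The change is a matter of wording, with no effect on care, visits or sample size. The statistical cost is the small precision gain that adjustment would bring if involvement independently predicted success and no failures were referred. In simulation, adjusting then raised power from 0.922 to 0.924-0.930 at an odds ratio of 2, and to 0.934-0.947 at an odds ratio of 4.
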